This research will enroll 225 adult smokers in a mixed design study with a withinsubjects factor (active nicotine patch vs. placebo patch) and a between-subjects factor (alternative products; VLNCs, Juul e-cigs, or no product). Participants will be randomized to receive either 4 weeks of VLNCs, 4 weeks of Juul e-cigs, or no alternative product. After one week practicing with the alternative product, participants will complete the first of two 7-day switching trials during which they will be asked to refrain from smoking their own cigarettes and encouraged to use the alternative product to which they have been assigned (although the no alternative product group will not have any other products to use). See Figure 3. All participants will be given 8 patches (active nicotine or placebo, in counterbalanced order, with one extra in case of mishaps) to use during the Switch Week. After this first Switch Week, they will smoke normally for one week and then have their second Switch Week using the other type of patch (active or placebo; see Figure 3). We opted to use a 7-day switching phase and only repeat it once to minimize the attrition that was problematic in other studies with longer experimental phases (e.g., three 10-day switching phases produced 45% attrition in the non-step down VLNC group¹¹²). Participants will complete ecological momentary assessments (EMAs) on smartphones at prior to and during the 4 weeks of product use. EMA targets include own cigarette use, alternative product use, withdrawal symptoms, rewarding value of product use (e.g., taste, buzz), and environmental and affective context of any tobacco product use. We will then conduct a 3-month follow-up to assess own cigarette and e-cig use, risk perceptions, and future use intentions. This design addresses the six critical methodological issues for understanding the impact of alternative products outlined by Villanti et al.¹¹³: 1) rigorously assesses the key outcome (conventional cigarettes smoked); 2) assesses product use during switching; 3) uses appropriate control/comparison groups; 4) measures product exposure/use that precedes switching; 5) evaluates the dose and duration of the product exposure/use; and 6) has clear evaluation of the type and quality of the products used (e.g., satisfaction).

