
"Understanding the real-world impact of the use of three alternate nicotine-delivery products on combustible cigarette use" PI: [name]; UW-CTRI Grant: R01CA239309

Participants will carry a smartphone to complete EMAs from Orientation through all 4 weeks of product use.

After providing consent at the Orientation visit, study staff will ask if the participant gives the study permission to stay in touch with them and send them reminders about upcoming study contacts during the study via email and/or text message. The staff member will remind them that email and text messaging are generally not a secure way to communicate about their health as there are many ways for unauthorized users to access email and text messages. The staff member will also inform them that they do not have to provide their email address or text message number to participate in this study.

Assessments

To address the primary aim of examining whether VLNCs and e-cigs serve as effective substitutes for conventional cigarettes, and whether use of these alternative products interacts with nicotine replacement, we will conduct extensive assessments of participants' use of their own cigarettes, their use of their assigned alternative products, use contexts, and potential motivators for such use behavior (e.g., withdrawal, reward value of products, risk perceptions). We will also assess person factors and beliefs that may provide insight into who is able and willing to use these alternative products to substitute for cigarettes and which mechanisms might be more relevant for which smokers. To the extent possible we will use measures from the PhenX Toolkit, a collection of broadly validated measures, to enhance the ability to harmonize data from this study with other studies. See Table 1 for the timing of assessments.

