Visit assessments. At each study visit, participants will complete assessments of affect using the well-validated Positive and Negative Affect Scale (PANAS¹²⁷), withdrawal symptoms using the validated Wisconsin Smoking Withdrawal Scale (WSWS¹²⁸), and craving using the Brief Questionnaire of Smoking Urges (QSU-Brief^{129,130}) from the PhenX Toolkit. At Visits 1 through 7 participants will complete the modified Cigarette Evaluation Scale (mCES^{71,131,132}) for cigarettes and at Visits 2 through 7 they will complete the mCES for their assigned alternative product based on their reactions in the last 24 hours. The 12 items of the mCES assess product satisfaction, psychological reward, aversion, enjoyment of respiratory tract sensations, and craving reduction. We will use timeline follow-back methods^{133,134} to assess daily use of participants' own cigarettes, assigned alternative products, and patch if the visit occurs during a Switch Week. These data will be used to supplement EMA reports in case of missing EMA data. Participants will also be asked at all visits except Visit 1 (when they will not have any study products or medication yet) about any possible adverse events from using VLNCs, e-cigs or the patches¹³⁵. At the final visit (Visit 7), we will again assess acceptability, risk perceptions, and

"Understanding the real-world impact of the use of three alternate nicotine-delivery products on combustible cigarette use" PI: [name]; UW-CTRI Grant: R01CA239309

intentions to use cigarettes, VLNCs, e-cigs, and patches. We will also assess how the Juul e-cig compares to other e-cigs participants have used, including what they like or do not like Juul, using a combination of questionnaires and open-ended questions to provide additional information regarding Juul acceptability among adults.

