own cigarette), there is approximately a 30% chance a more comprehensive assessment (3) minutes) will be triggered that will include: 1) time since prior use of cigarette/alternative product), 2) use context (e.g., smoking prohibited, others vaping/smoking, home, work), activity, and withdrawal symptoms and affect prior to use, and 3) individual items from the mCES that tap potential mechanisms (e.g., product satisfaction, psychological reward, aversion, enjoyment of respiratory tract sensations, and craving reduction). The comprehensive assessments will be specific for each type of use event (i.e., cigarettes, VLNCs, and e-cigs). All participants will complete an evening assessment prior to going to bed. Evening reports (5 minutes) will assess: affect, withdrawal, use of cigarettes and alternative products, overall satisfaction with cigarettes/alternative products, use of patch during Switch Weeks, smoking cues, stressors, and pleasure in daily activities. Participants will spend less than 25 minutes each day recording use events and answering questions, eliminating the problems of recall bias or participants prefilling or back-filling a traditional daily diary. This approach is more rigorous than relying on participants to document their use of non-experimental products using a paper and pencil log¹⁴². We have conducted numerous EMA studies and will use the strategies that have been successful in our earlier work: training in assessments, ability to briefly postpone assessments, use of counters, etc.^{50,86,143}. This frequency of assessment is of moderate intensity relative to protocols used in our prior work⁸⁶.

Follow-up assessment call. Three months after Visit 1, participants will complete a brief follow-up assessment call to assess current smoking, use of any alternative products, motivation and self-efficacy for smoking cessation, risk perceptions, and future plans to use VLNCs, e-cigs, and patches.

Participants who are interested in quitting smoking after Visit 7 will be offered the Wisconsin Tobacco Quit Line toll-free number? ([name]) and the phone number(s) for smoking cessation studies being conducted at our Center.

Alternative Products and the Nicotine Patch

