All study products (nicotine and placebo patches, JUUL e-cigarettes, and very low nicotine cigarettes) will be received from vendors at the Center for Tobacco Research and Intervention Madison office. Products stored in a locked room or cabinet at the Madison and Milwaukee research sites until processed and portioned for dispensing. Dissemination bags containing processed study product will be labeled with Study ID and participant initials and stored in secure, locked cabinets, closets or rooms in Madison and Milwaukee. Study staff with no contact with participants will process and portion out the study products to maintain the double-blind on the patches. Participants will be asked to return all unused patches, VLNCs and JUUL pods as well as the JUUL device at the end of the study. Participants in the JUUL condition will also be asked to return used JUUL pods at each study visit.

Promoting Continued Experimental Participation

We will promote participation and adherence to study procedures using strategies that were effective in our prior research. We will: 1) allow flexibility in scheduling¹⁴⁴⁻¹⁴⁶; 2) provide participants with a single, consistent liaison^{144,147,148}; 3) ensure that research staff are culturally sensitive^{149,150}; 4) send reminder letters prior to the Month 3 follow-up call and make reminder calls to remind participants about their Orientation Visit and Visits 1, 2 and 5; and 5) compensate participants for their time¹⁴⁷. Specifically, participants will be paid \$20 for completing each of the 8 study visits and the 3-month follow-up call (up to \$180), and \$200 for completing 80% of the EMA prompts or \$150 for completing 75% of the EMA prompts.

"Understanding the real-world impact of the use of three alternate nicotine-delivery products on combustible cigarette use" PI: [name]; UW-CTRI Grant: R01CA239309

Participants may receive up to \$380 in total compensation. Finally, participants will be invited to share their email or mailing address to receive a copy of the final research results.

Analytic Plan

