The primary aim of this research is to examine the ability of VLNCs and e-cigs to substitute for smokers' usual cigarettes compared to each other and to no alternative product use (Product between-subjects effects) and whether these effects are influenced by steadystate nicotine (Patch within-subjects factor; active vs. placebo patch). The primary analysis model will consist of a mixed analysis of variance (ANOVA) with three levels of the Product between-subjects factor (VLNCs, e-cigs, no alternative product) and two levels of the Patch within-subjects factor (active nicotine patch, placebo patch). To address the primary aim, we will explore statistically significant main or interaction effects in the mixed ANOVA by means of unadjusted simple main effects, interaction contrasts, and pairwise comparisons^{156,157}. Specifically, we will examine the main effect of Product to evaluate the hypothesis that participants who do not have an alternative product will report smoking significantly more of their own cigarettes during the Switch Weeks compared to those who have VLNCs or e-cigs. We will also conduct a pairwise comparison to explore whether there is a significant difference in the number of conventional cigarettes smoked in the VLNC vs. e-cig conditions. We will use the main effect of Patch (active vs. placebo) to evaluate the hypothesis that participants will report smoking fewer of their own cigarettes during Switch Weeks when they receive active nicotine patches compared to placebo patches. We will also test the Patch x Product interaction, with follow-up pairwise comparisons, to examine whether steady-state nicotine produces a differential effect on the number of conventional cigarettes smoked, based on which alternative product a participant was assigned to receive.

The primary outcome is the number of conventional cigarettes smoked during each Switch Week. Based on the literature and our own research, it is possible this outcome will not be normally distributed (i.e., a substantive proportion of participants may smoke no conventional cigarettes during a Switch Week). Therefore, prior to conducting main analyses, we will examine the distributional characteristics of the primary outcome to determine if a transformation is needed (e.g., if the distribution substantially deviates from a normal distribution).

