and mechanisms variables will be based on means across the 7 days of the Switch Weeks. For these summary outcomes, we will use statistical models similar to the analyses described above for the primary outcome. For the ILD outcomes, we will create one set of outcomes based on the evening report that assesses experiences across the full day and another set based on the 3 quasi-random comprehensive assessments that occur during the day. For the ILD versions of the outcomes, we will use conditional growth curve models that permit slope and intercept parameters to be evaluated across the 7 days of the Switch Weeks as a function of group; these models also permit examination of other forms of change over time (e.g., linear, quadratic, cubic). We will explore two main approaches to growth curve modeling: a multilevel modeling (MLM) approach¹⁵⁸ and a structural equation modeling (SEM) approach¹⁵⁹. Although similar, each of these modeling approaches has advantages and disadvantages¹⁶⁰ that we will exploit in exploratory analyses. While we are not powered to detect mediation due to funding limitations, we will conduct exploratory mediation analyses to provide information for future research on whether these mechanisms mediate the effects of alternative product use on the use of conventional cigarettes.

Power for Primary Aim Hypotheses

With attrition-adjusted n=54 per group for a between-subjects pairwise comparison, the study is powered to detect a difference of 3.3 cigarettes (SD=6); a corresponding within-subjects pairwise comparison (SD=6, correlation=0.5) is powered to detect a difference of 2.8 cigarettes. Thus, we feel that a total N=225 provides adequate power to detect predicted effects.

Protection of Human Subjects

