mobile devices that are provided to subjects are deployed with password protection, MDM software, encryption, and other lockdown features. Each device returned to UW-CTRI from subjects are wiped and factory reset, then redeployed with the above features and then minimal features to complete data collection per study design. The minimal features that are enabled on each device are phone, text messenger and data collection app. There will be no data stored on the UW-CTRI mobile devices, it will be directly transferred from the app to a secure UW-CTRI server.

As stated above, no data are stored on individual computer hard drives. All data are transmitted from the point of collection to the UW-CTRI server through secure, encrypted web connection. On those rare occasions when, due to a loss of internet access or computer hardware failure, data are collected in paper forms, these forms will be stored securely at UW-CTRI until the data are able to be entered into the database and the paper document will then be disposed of securely. No identifying data other than a participant ID number is entered on any data form. Consent forms are obtained in paper copy; these forms contain the participant name and signature. These are retained in secure files at the clinic where they are collected and then transported to the UW-CTRI office, where they are securely stored.

Finally, no publications or presentations resulting from this research program will contain any identifying information about individual participants.

Potential Benefits of the Proposed Research to the Participants and Others

There are no specific benefits for smokers participating in this study, beyond the benefit of helping inform scientists and FDA regulators about the ability of these alternative products to serve as substitutes for conventional cigarettes and whether this is influenced by the presence of steady-state nicotine.

Importance of the Knowledge to be Gained

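### The primary mixed ANOVA does not say how a participant with only one Switch Week count is analysed; a mixed model on all available weeks would keep those data and is the better choice at small cost

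*Combined protocol and SAP*

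**What the plan says.** The Analytic Plan gives one primary model: "The primary analysis model will consist of a mixed analysis of variance (ANOVA) with three levels of the Product between-subjects factor" and two levels of the Patch within-subjects factor. The outcome is the count of own cigarettes in each Switch Week. The section names no estimator and no analysis set, and gives no treatment for a participant with one count out of two. Multilevel models appear only for the exploratory daily EMA outcomes.

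Loss is expected. Power for Primary Aim Hypotheses begins "With attrition-adjusted n=54 per group for a between-subjects pairwise comparison", without saying when the loss occurs or how those lost are handled.

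There is a provision for incomplete recording. Under Visit assessments, timeline follow-back collects daily own-cigarette use: "These data will be used to supplement EMA reports in case of missing EMA data". The app data themselves are extensive:
- Study Visits and Phone Contacts: "Participants will carry a smartphone to complete EMAs from Orientation through all 4 weeks of product use".
- Ecological momentary assessments: "Evening reports (5 minutes) will assess: affect, withdrawal, use of cigarettes and alternative products".
- Protection Against Risk, on app data: "it will be directly transferred from the app to a secure UW-CTRI server".

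A missed visit is therefore not a missed week. The text does not cover days absent from both sources, or how many days make a valid week.

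Citations run to 150 in Promoting Continued Experimental Participation and resume at 156 in the Analytic Plan. References 151 to 155 (missing-data and longitudinal methods, and a modelling-software manual) are listed but not cited in the text supplied.

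**The concern.** A conventionally fitted mixed ANOVA needs both cells for every participant. Someone who completes Switch Week 1 and then stops reporting, without returning for a later follow-back, would leave the primary analysis with a valid count in hand. The primary question compares randomised Product arms, so discarding randomised participants after the first outcome puts that comparison at some risk.

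The precision lost is already allowed for in the sample size. What remains at stake is a conditional bias. If those who leave smoke more (or less) than those who stay, and this differs by arm, the completers' contrast shifts. The plan gives some reason to think loss could differ by arm. The opening overview cites an earlier study in which "three 10-day switching phases produced 45% attrition in the non-step down VLNC group". Protection Against Risk also has a discontinuation rule, tied to amount smoked or exhaled CO, that applies to the VLNC arm only. That rule is not questioned here, but the plan does not say whether data already collected from those participants are kept. Leaving the handling open also lets it be chosen after results are seen.

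**Working it through.** **Inputs.** From the plan: total 225; 54 analysable per group; SD 6; correlation 0.5; difference 3.3. The plan does not say whether 3.3 and 6 are per day or per week, so results are in the plan's units. Assumed: 75 per arm, two-sided 5% test, and every dropout mechanism below.

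**Plan's own figure.** SE = 6 × √(2/54) = 1.155. 3.3/1.155 = 2.86, and Φ(2.86 − 1.96) gives 81.5% power (80.8% by noncentral t). The 3.3 reproduces.

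**Implied loss.** 54/75 = 0.72, so 28%, or 21 of 75 per arm.

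**Precision of the Product contrast averaged over both weeks, loss unrelated to smoking.**
- Completers: variance per arm 36 × (1 + 0.5)/2 ÷ 54 = 27/54 = 0.50; SE = √(0.50 + 0.50) = 1.00; power at 3.3 about 91%.
- All available weeks, k one-week participants per arm: information 54 × 2/(36 × 1.5) + k/36 = 2 + k/36; SE = √(2/(2 + k/36)).
 - k = 0: 1.00.
 - k = 10: 0.94.
 - k = 21: √(2/2.583) = 0.88; power about 96%.
- With no missing weeks the two Product estimates are the same.

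**Bias of the completers' contrast.** Let the log-odds of loss after Switch Week 1 rise by b per SD of Switch Week 1 smoking, with overall loss p. Among those who stay, the standardised Week 1 mean falls by b × E[q(1 − q)]/(1 − p), where q is the individual loss probability. The two-week mean moves by 6 × (1 + 0.5)/2 = 4.5 times that.

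Slope in the no-product arm only, p = 0.28:
- b = 0.5: E[q(1 − q)] = 0.192; shift 4.5 × 0.5 × 0.192/0.72 = 0.60; estimate 3.3 − 0.60 = 2.70.
- b = 1.0: E[q(1 − q)] = 0.171; shift 4.5 × 0.171/0.72 = 1.07; estimate 2.23.
- Type I error with SE 1.00: Φ(−1.96 + 0.60) + Φ(−1.96 − 0.60) = 9.2%; with 1.07, about 19%. Simulation gives 9.3% and 19.1%.

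Other patterns (completers, b = 0.5 / 1.0, true 3.3):
- slope in the product arm only: 3.89 / 4.36;
- same slope in both arms, 18% (no-product) vs 38% (product) loss: 3.71 / 4.01;
- equal loss and equal slopes: 3.30;
- unequal loss unrelated to smoking (19.3% vs 45%): 3.27, no real bias.

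The mixed model gives 3.27 to 3.31 in the biased patterns above, with type I error near 5%.

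**Where the mixed model falls short.** If loss in the no-product arm depends on unseen Switch Week 2 smoking, it gives about 3.1 at slope 0.5 and 2.7 to 2.9 at slope 1.0, against completers' 2.7 and 2.2. That recovers roughly half to three-fifths of the bias. People lost before any Switch Week data contribute nothing to either analysis.

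**The case against.** Several points on the other side stand.

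- A reader might infer that the plan will delete one-week participants. It does not say so; listwise deletion is the convention for this model, not a stated rule.
- A reader might infer that the plan has no missing-data handling. Follow-back does supplement missing app data. The uncited references 151 to 155, and a pointer in the text to a section A.5.1 that is not in it, suggest that handling text may exist elsewhere. That is suggestive, not proof.
- A reader might take payment "for completing 75% of the EMA prompts" as evidence that days will go unrecorded. It is not. Payment concerns prompts, while own cigarettes are logged by button press, again in the evening report, and again at visits.
- The 45% attrition comes from a longer design that this trial was built to avoid. It is not a forecast, and the VLNC discontinuation rule has no stated frequency.
- The dropout slopes have no source in the documents. At slope 0.5 every shift is about 0.3 to 0.6, below one standard error, and even the direction is unknown.
- The main cases assume that everyone lost first supplies Switch Week 1, which favours the mixed model. If half the loss comes earlier and also depends on smoking in the no-product arm, the mixed model gives 3.00 / 2.73 against completers' 2.66 / 2.14, so about half of the bias remains.

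These points limit the claim. They do not supply a rule for the one-week participant, and they give no reason to prefer a model that discards a valid count.

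**Conclusion.** The point holds in limited form. The only primary model named leaves the one-week participant unaddressed while the plan budgets for about 28% loss (equal allocation assumed). A likelihood-based mixed model on all available weeks is a better primary analysis: the Product estimate is the same with complete data, and the standard error is between 0.88 and 1.00 instead of 1.00 under 28% loss, depending on how many of those lost give a usable week.

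Two stronger readings are not supported. The documents do not show that the Product comparison is biased: that needs loss related to smoking and differing by arm in rate or pattern, and no loss by arm or week is given. Nor would the mixed model protect the comparison unconditionally: it reduces bias to the extent that loss depends on recorded smoking. For partly recorded weeks the gap is confined to days missing from both the app and follow-back; the plan nowhere proposes counting such days as zero. This should be fixed; confidence is medium because the size of any bias rests on assumed dropout.

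**What to change.** Make the primary analysis a linear mixed model fitted by REML, with a random participant intercept and fixed Product, Patch, Product × Patch and period (first or second Switch Week). The period term matters because one-week participants mostly contribute the first week. Include every randomised participant with at least one Switch Week count, analysed as randomised, and keep observed data from anyone discontinued. Use the transformed scale if one is adopted. Take all planned tests and pairwise contrasts from this model.

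State in advance that a day missing from both the app and follow-back is not counted as zero, and set a minimum number of days for a valid week (for example 4 of 7, scaled to 7).

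Report as sensitivity analyses the completers' mixed ANOVA and one shift-based analysis for outcome-related dropout. Tabulate loss by arm and timing. If handling text matching references 151 to 155 exists elsewhere, restore it and align it with this model.

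The cost is analysis-plan wording, a different software procedure and two extra analyses; no new data are needed, and the plan already intends multilevel models for the EMA outcomes. The downside is the missing-at-random assumption, and scaling a partial week assumes recorded and unrecorded days are alike.
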